12.1.3 Occurrence of adverse events and adverse drug reactions

The number of subjects experiencing events and the incidence of events will be presented for all events and by primary SOC and PT.

12.1.4 Occurrence of adverse events and adverse drug reactions (by severity)

The numbers of events by severity will be presented for all events and by primary SOC and PT.

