Reported serious adverse events included the following: 2 events (encephalopathy and shunt stenosis) in 2 subjects in the 0.25 μ g/kg group, 8 events (abdominal distension, influenza, diverticulitis, dizziness, hyperglycaemia, cholecystitis, hypotension, and muscular weakness) in 4 subjects in the 0.5 μ g/kg group, and 1 event (dizziness) in 1 subject in the 1.5 μ g/kg group. Of these events, relationship to study treatment was not ruled out for 4 events (diverticulitis, dizziness, hypotension, and hyperglycaemia) in 3 subjects in the 0.5 μ g/kg group and 1 event (dizziness) in 1 subject in the 1.5 μ g/kg group. Study treatment was discontinued or interrupted due to 1 event in 1 subject in the 0.25 μ g/kg group, 2 events in

2 subjects in the 0.5 μ g/kg group, 1 event in 1 subject in the 1.0 μ g/kg group, and 17 events in 10 subjects in the 1.5 μ g/kg group. Dependency was assessed as being present in 2 subjects in the placebo group and 1 subject in the MR13A9 0.5 μ g/kg group.

In a non-Japanese phase II clinical study (CR845-CLIN2005 Part B), 65 hemodialysis patients with moderate to severe pruritus received intravenous doses of MR13A9 1.0 μ g/kg or placebo 3 times weekly for 2 weeks. With respect to efficacy, the primary endpoint of change in VAS (i.e., change from baseline in the mean VAS for the most intense itching at Week 2) (mean \pm standard deviation) was -33.1 ± 23.03 mm in the 1.0 μ g/kg group versus -21.5 ± 24.79 mm in the placebo group. With respect to safety, the incidence of adverse drug reactions was 9.4% (3/32 subjects) in the placebo group and 18.2% (6/33 subjects) in the 1.0 μ g/kg group. Commonly reported adverse drug reactions (in \geq 5% of subjects in the MR13A9 group) included dizziness, hypoaesthesia, and pruritus.

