9.12.3 Severity of adverse events

The severity of adverse events will be categorized into 3 grades according to Table 9.12.3-1. For an adverse event in which the severity changes, the highest severity will be recorded.

Table 9.12.3-1 Severity of adverse events

Severity	Criteria
Mild	Not or minimally interfering with daily activities ^{a)} and requiring no special treatment or simple
	treatment

Moderate	Somewhat interfering with daily activities ^{a)} and requiring treatment
Severe	Largely interfering with daily activities ^{a)} or requiring systemic treatment

a) Include sleeping, movements, work, going out, eating, exercise, bathing

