12.1 Adverse Events and Adverse Drug Reactions

Unless otherwise specified, the following events will be tabulated.

- Events occurring between the start of study treatment and the end of the follow-up period
- Events occurring between the start of study treatment and the end of the treatment period
- Adverse events of special interest occurring between the start of study treatment and the end of the follow-up period
- Adverse events of special interest occurring between the start of study treatment and the end of the treatment period

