12.1.1 Incidence of adverse events and adverse drug reactions

The number of events, the number of subjects experiencing events, the incidence of events and its two-sided 95% confidence interval will be presented. Fisher's exact test will be used for comparisons between the placebo group and each of the MR13A9 0.25, 0.5, and 1.0 μ g/kg groups. The difference in the incidence between the placebo group and the MR13A9 0.25, 0.5, and 1.0 μ g/kg groups and its two-sided 95% confidence interval will be presented.

12.1.2 Incidences of adverse events and adverse drug reactions (serious adverse events, adverse events leading to discontinuation of treatment period, and adverse events of special interest)

For adverse events occurring between the start of study treatment to the end of the follow-up

Protocol No. MR13A9-4 Version: 1.0

period, and adverse events between the start of treatment with the study drug to the end of the treatment period, the number of events, the number of subjects experiencing events, and the incidence of all events, adverse events leading to death, serious adverse events excluding death, events leading to interruption, events leading to discontinuation of the treatment period, and adverse events of special interest will be presented.

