12.1.5 Details of adverse events of special interest

For adverse events of special interest occurring between the start of the study treatment to the end of the follow-up period, the number of events, the number of subjects experiencing events, and incidence of adverse events and adverse drug reactions will be presented, and the number of events for each category in Table 12.1.5-1 will be presented.

Table 12.1.5-1 Analysis Items

Tallette 1 - 1 - 1 - 1 - 1 - 1 - 1 - 1 - 1 - 1		
Item	Category	
Severity	Mild, moderate, severe	
Action taken with study treatment	Drug withdrawn, drug interrupted, dose not changed, unknown, not applicable	
Outcome	Recovered/resolved, recovering/resolving, not recovered/not resolved, recovered/resolved with sequelae, fatal, and unknown	
The period of recovered/resolved	Treatment period, follow-up period or later	

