12.4 Dependency Assessment

12.4.1 Evaluation of dependency based on judgment by dependency assessment members

The numbers and percentages of subjects will be presented by category in Table 12.4.1-1. However, only subjects with dependence will be included in the tabulation of severity.

Table 12.4.1-1 Category

Item	Category
Dependency	Negative, positive, not evaluable
Severity	Mild, moderate, severe

Statistical Analysis Dlan	Protocol No. MR13A9-4
Statistical Analysis Plan	Version: 1.0

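### Adverse event severity is tabulated only as numbers of events, so the proportion of subjects with a moderate or severe event at each dose is produced nowhere

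*SAP*

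**What the plan says.** **Severity tables.** For all adverse events and adverse drug reactions, SAP 12.1.4 states: "The numbers of events by severity will be presented for all events and by primary SOC and PT". Protocol 13.6.1 item 4 uses the same wording. For events of special interest, SAP 12.1.5 gives subjects and incidence for these events taken together. For the mild, moderate and severe rows it says only that "the number of events for each category in Table 12.1.5-1 will be presented".

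**Event sets.** SAP 12.1 opens with "Unless otherwise specified, the following events will be tabulated" and names four sets: all events and events of special interest, each to the end of follow-up and to the end of treatment. None of the four adds a severity table that counts subjects.

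**Subject-level tables.** SAP 12.1.1 gives overall incidence with 95% CI, Fisher tests and differences from placebo. SAP 12.1.2 gives events, subjects and incidence for deaths, other serious events, "events leading to interruption, events leading to discontinuation of the treatment period, and adverse events of special interest will be presented". SAP 12.1.3 reads: "The number of subjects experiencing events and the incidence of events will be presented for all events and by primary SOC and PT". SAP 12.5 repeats the 12.1.1 analysis in subgroups.

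**Severity at data collection.** Protocol 9.12.3 grades events as mild, moderate or severe and adds: "For an adverse event in which the severity changes, the highest severity will be recorded".

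**The concern.** Protocol section 3 makes the dose-response relationship for safety an objective alongside efficacy. A reader comparing 0.25, 0.5 and 1.0 μg/kg with placebo will want to know what proportion of subjects had a moderate or severe event in each group. Event counts do not answer that. Events within one subject are not independent, a count has no subject denominator, and it gives no proportion or interval to set against placebo.

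Several events per subject are to be expected here. Specific signs and symptoms are asked about every week (protocol 9.12.5). The protocol also provides for an event secondary to another event to have its own causality assessment (9.12.8).

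Events of special interest make the gap more visible. Protocol 3.2.2 sets them up so that central nervous system effects can be assessed with care, and protocol 1.4.1 describes such reactions in the earlier Japanese study by their severity. In this trial their severity would be shown without a subject denominator.

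**Working it through.** The plan states no figure on this point, so there is none to reproduce. The check is first of the text, then of what an event count can and cannot show.

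**Step 1: unit of count in each output**

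| Output | Counts subjects? | Split by adverse event severity? |
|---|---|---|
| SAP 12.1.1 overall incidence | yes | no |
| SAP 12.1.2 death, other serious, interruption, discontinuation, special interest | yes | no |
| SAP 12.1.3 by SOC and PT | yes | no |
| SAP 12.1.4 by severity | no | yes |
| SAP 12.1.5 special interest, together | yes | no |
| SAP 12.1.5 special interest, severity rows | no | yes |
| SAP 12.5 subgroups | yes | no |

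No row has yes in both columns.

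**Step 2: two provisions that might seem to fill the gap**

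- The highest-severity rule in protocol 9.12.3 works within a single event. It does not take the worst grade across all of a subject's events.
- SAP 12.4.1 counts subjects by severity, where "only subjects with dependence will be included in the tabulation of severity". That is severity of dependency, not of adverse events.

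**Step 3: what an event count implies**

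Input: 60 subjects per group (protocol 7.6.1). Assumption for illustration: 12 severe events in one group. Proportion of subjects = subjects with at least one severe event ÷ 60.

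- One event each: 12/60 = 20.0%
- Two events each: 6/60 = 10.0%
- Four events each: 3/60 = 5.0%

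The 12.1.4 table prints 12 in all three cases. Suppose further, also as an assumption, that placebo has 3 severe events in 3 subjects (3/60 = 5.0%). The difference in proportions is then 15, 5 or 0 percentage points, while the table shows 12 events against 3 throughout.

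**Step 4: can the planned tables be combined to recover the proportion?**

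Let S be the subjects with any event, E the severe events and F the other events. The number of subjects with a severe event is at most min(E, S). It is at least max(1, S − F) when E is 1 or more. The lower limit falls to 1 whenever F is as large as S or nearly so. With E = 12 and S at least 12, the widest range is 1/60 = 1.7% to 12/60 = 20.0%. Only cells with 0 or 1 event are unambiguous.

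**The case against.** **What stands**

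- The most consequential events do have subject denominators. SAP 12.1.2 counts subjects with fatal, serious, interrupting, discontinuing and special-interest events, and SAP section 13 lists them. If those lists carry the grade, worst severity could be worked out by hand for these events. No list of all adverse events is planned.
- Safety dose-response is not left without subject-level output. SAP 12.1.1 gives incidence with intervals and differences from placebo. Only the severity split is missing.
- Severe cells may be sparse. Protocol 1.4.1 says central-nervous-system-type reactions in the earlier Japanese study were mostly mild and never severe. If so, the ambiguity falls mainly on moderate events.
- Protocol and SAP agree, and no rule is broken. Protocol section 13 allows further necessary analyses at the discretion of the statistical analysis manager, so the table could be produced without an amendment.

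**Stronger readings that the documents do not support**

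- *A size taken from MR13A9-3.* Protocol 1.3.2.2 reports serious events as "8 events (abdominal distension, influenza, diverticulitis, dizziness, hyperglycaemia, cholecystitis, hypotension, and muscular weakness) in 4 subjects in the 0.5" μg/kg group, and 17 events in 10 subjects leading to discontinuation or interruption at 1.5 μg/kg. A reader might infer that counts inflate arm differences up to twofold. These are serious and discontinuation or interruption events, not severity grades, and SAP 12.1.2 already counts such events by subject. The 1.5 μg/kg dose is not in this trial. At 0.25, 0.5 and 1.0 μg/kg, discontinuation or interruption ran at one event per subject (1 in 1, 2 in 2, 1 in 1). Nor is twofold a limit: serious events at 0.5 versus 0.25 μg/kg differ by 8 − 2 = 6 events but 4 − 2 = 2 subjects, which is threefold. The figures show that events can cluster; they do not size this problem.
- *Bias from early stopping.* Subjects who stop early contribute fewer events, but they also have less time to reach a worse grade. Crude percentages by worst severity depend on time in study too, so this argument does not favour either table.
- *Tolerability decides the dose.* Protocol 7.2.4 says efficacy and safety profiles together will inform the recommended doses. It states no severity criterion.

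**Conclusion.** The gap is real and minor. Adverse event severity is tabulated only as numbers of events in SAP 12.1.4, protocol 13.6.1 item 4 and the severity rows of SAP 12.1.5. No planned output gives the proportion of subjects with a moderate or severe event at each dose.

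The textual finding rests on no assumption. Its practical size cannot be derived from the documents, which give no events-per-subject data by severity grade. The 20%, 10% and 5% illustration shows what a count of 12 in a group of 60 leaves open; it does not predict what will be seen. If nearly every affected subject has a single event at a given grade, the two tables will agree and nothing is lost. The primary efficacy analysis is untouched.

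**What to change.** Keep the event counts, which the protocol prespecifies, and add to them:

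1. In SAP 12.1.4, the number and percentage of subjects by worst severity, each subject counted once, overall and by SOC and PT (within a SOC or PT row, at that subject's worst grade in the row).
2. The same columns for the severity rows of SAP 12.1.5.
3. For moderate-or-worse events overall, from start of treatment to end of follow-up, the difference in incidence between each dose and placebo with its 95% CI by the 12.1.1 method, labelled descriptive.

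Record the addition in SAP section 2, as was done for the special-interest tabulation.

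**Cost.** Longer tables and a few extra unadjusted descriptive intervals. Item 3 for adverse events and adverse drug reactions gives 3 doses × 2 = 6 intervals. Applying it to all four event sets in SAP 12.1 would give 6 × 4 = 24, which is why one window and one set are enough. Severity is already recorded for each event after the start of treatment (protocol 9.12.1), so no new data are needed. Alpha, power and sample size do not change.

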12.1.5 Details of adverse events of special interest

For adverse events of special interest occurring between the start of the study treatment to the end of the follow-up period, the number of events, the number of subjects experiencing events, and incidence of adverse events and adverse drug reactions will be presented, and the number of events for each category in Table 12.1.5-1 will be presented.

Table 12.1.5-1 Analysis Items

Tallette 1 - 1 - 1 - 1 - 1 - 1 - 1 - 1 - 1 - 1		
Item	Category	
Severity	Mild, moderate, severe	
Action taken with study treatment	Drug withdrawn, drug interrupted, dose not changed, unknown, not applicable	
Outcome	Recovered/resolved, recovering/resolving, not recovered/not resolved, recovered/resolved with sequelae, fatal, and unknown	
The period of recovered/resolved	Treatment period, follow-up period or later	

12.2 Laboratory Tests

Analysis items are shown below.

Laboratory tests: Red blood cell count, hemoglobin, hematocrit, white blood cell count, differential white blood cell count (neutrophil, eosinophil, basophil, monocyte, lymphocyte), platelet count, AST, ALT, γ-GTP, CRP, LDH, ALP, total protein, albumin, glycoalbumin, glucose, total cholesterol, total bilirubin, direct bilirubin, creatinine, BUN (before dialysis), Na, K, Cl, Ca, P, serum iron, UIBC, TIBC, TSAT, ferritin, testosterone, free testosterone, prolactin, TSH, FT3, FT4, intact-PTH, antidiuretic hormone

12.2.1 Laboratory tests

Summary statistics will be presented.

Assessment time points: Weeks -2, 0, 1, 2, 4, and 8, end of the treatment period, and Follow-up Week 2

Statistical Analysis Plan Protocol No. MR13A9-4 Version: 1.0

12.2.2 Shift table of laboratory data

The numbers and percentages of subjects with low, normal, or high values before and after administration will be presented.

Assessment time points: Week 0 and end of the treatment period

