3.2.2 Rationale for the safety endpoints

In addition to the endpoints generally used for safety evaluation, endocrinology testing and dependency assessment have been selected because these endpoints could be affected by opioids. In addition, for careful assessment of their effects on the central nervous system, adverse events of special interest have been established.

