All statistical tests will be performed using a two-sided significance level of 5%; however, a two-sided significance level of 15% will be used for the analysis of between-group imbalance. Summary statistics will be presented as the number of subjects, mean, standard deviation, minimum, median, maximum, and quartile. Unless otherwise specified, data will be tabulated by group and by time point. Week 0 will be the baseline.

SAS System Release 9.4 for Windows (SAS Institute Inc.) will be used to conduct the analysis.

4. Analysis Sets

The analysis sets are defined as follows. When the full analysis set (FAS) and the per protocol set (PPS) are used as analysis sets, analyses will be performed based on the treatment group to which each subject has been allocated. When the safety set (SS) and the pharmacokinetic analysis set (PKS) are used as analysis sets, analyses will be performed based on the treatment group in which each subject has been actually treated.

- FAS: Population of subjects, excluding the following subjects: subjects with GCP violations, untreated subjects, discontinued subjects before entry to the treatment period, some of the ineligible subjects, and subjects with no available mean NRS score at baseline (Week 0)
- PPS: Population of subjects, excluding the following subjects from the FAS: ineligible subjects, discontinued subjects, deviators, and subjects with broken emergency key codes, as the subjects to be excluded from the PPS

Statistical Analysis Plan	Protocol No. MR13A9-4
	Version: 1.0

- SS: Population of subjects, excluding the following subjects: subjects with GCP violations, untreated subjects, and discontinued subjects before entry to the treatment period
- PKS: Population of subjects, excluding the following subjects from the SS: subjects with no available plasma drug concentration data

Correspondence of the analysis items and the analysis sets is shown in Table 4-1.

Table 4-1 Analysis Items and Analysis Sets

Endpoints	Analysis items	Analysis sets
Demographic and other baseline	Subject demographics	FAS, PPS, SS, PKS
characteristics	Other	SS
Treatment compliance	All items	FAS, SS
Efficacy	Primary variable (primary analysis)	FAS (primary analysis set), PPS
	Other	FAS
Pharmacokinetics	All items	PKS
Safety	All items	SS

5. Analysis Groups

- MR13A9 0.25 μg/kg group: Subjects allocated to or treated with MR13A9 0.25 μg/kg
- MR13A9 0.5 μg/kg group: Subjects allocated to or treated with MR13A9 0.5 μg/kg

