12.5 Safety Subgroups

The same analysis as "12.1.1 Incidence of adverse events and adverse drug reactions" will be performed for each subgroup shown in Table 12.5-1.

Table 12.5-1 Subgroups

Item	Category
Sex	Male, female
Age	< 65 years, ≥ 65 years
Prior treatment with nalfurafine hydrochloride	No, Yes
Specific signs or symptoms to be confirmed in the screening period	No, Yes

13. Tabulated Lists

The following lists will be prepared for subjects who entered the treatment period. However, the lists will not be prepared if there is no applicable event.

- Deaths
- Serious adverse events excluding deaths
- Adverse events leading to interruption
- Adverse events leading to discontinuation during the treatment period
- Adverse events of special interest
- Abnormal laboratory values by subject

14. History of Preparation

Prepared on January 20, 2020 Version: 1.0

CERTIFICATE OF TRANSLATION

This document is the translated version of the source document below written in Japanese. It is hereby certified that this document is a true and accurate translation of the source document from Japanese into English.

Source document: MR13A9-4 Statistical Analysis Plan (Ver 1.0)

File name: mr13a9-4-s-jp-p.pdf

Name of representative:

Signature and Date of signature: Refer to Signature Page

SIGNATURE PAGE

Document ID: 090186a1801125b5

User	Date(UTC)	Reason
		,

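### Endocrine shift tables compare Week 0 with the final treatment sample only, and testosterone is summarised with the sexes pooled, so early abnormal values not reported as adverse events have no count by dose and a testosterone effect in men is diluted

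*SAP*

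**What the plan says.** Protocol 3.2.2 gives the reason for measuring hormones: "endocrinology testing and dependency assessment have been selected because these endpoints could be affected by opioids". Protocol section 3 includes safety in the dose-response objective. Protocol 10.5, 10.6, 10.8 and 10.11 schedule endocrinology at Weeks 1, 2, 4 and 8 (or at discontinuation).

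The SAP analyses these tests as follows.

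- **Items (12.2).** The list includes "testosterone, free testosterone, prolactin, TSH, FT3, FT4, intact-PTH, antidiuretic hormone".
- **Summaries (12.2.1).** Summary statistics only, at "Weeks -2, 0, 1, 2, 4, and 8, end of the treatment period, and Follow-up Week 2". No change from baseline is named.
- **Shift tables (12.2.2).** "The numbers and percentages of subjects with low, normal, or high values before and after administration will be presented". The time points are "Assessment time points: Week 0 and end of the treatment period". The scatterplots in 12.2.3 use the same two points.
- **Layout (section 3).** "Unless otherwise specified, data will be tabulated by group and by time point". Nothing in 12.2 specifies a split by sex.
- **Sex subgroup (12.5).** Sex is a safety subgroup, but only the overall incidence of adverse events and adverse drug reactions is repeated within it.
- **Listing (section 13).** Abnormal laboratory values are listed by subject, with no limit to the last sample.

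Protocol 9.12.1.3 makes a laboratory abnormality an adverse event when the investigator considers it clinically significant. SAP 12.1.3 tabulates such events by preferred term.

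**The concern.** The low/normal/high shift table is the only planned count by dose that rests on measured laboratory values alone. For a completer it uses the Week 8 sample and leaves out Weeks 1, 2 and 4. The programme's own endocrine signal arose early: study MR13A9-3 dosed for only 2 weeks and reported TSH decreased and prolactin increased among its common adverse drug reactions (protocol 1.3.2.2).

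If a change appears early and settles under continued dosing, the dose-response for abnormal hormone values rests on investigator judgement, because the table built on measured values would show those subjects as normal.

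Testosterone raises a second issue. Men and women have very different levels, sex is not one of the two allocation factors (protocol 7.5.4.4), and the summaries give neither a split by sex nor a within-subject change. A fall confined to men is averaged with women who contribute almost nothing, against a standard deviation inflated by the gap between the sexes.

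**Working it through.** **1. The documented signal.** From protocol 1.3.2.2, TSH decreased as an adverse drug reaction: 2/21 = 9.5% at 0.25, 6/19 = 31.6% at 1.0 and 7/23 = 30.4% at 1.5 µg/kg. Prolactin increased: 1/19 = 5.3% at 1.0 and 4/23 = 17.4% at 1.5 µg/kg. The protocol's percentages are reproduced.

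**2. Where an abnormal Week 2 TSH that is normal at Week 8 would appear.**

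| Output | Shown? | Gives incidence by dose? |
|---|---|---|
| Shift table, SAP 12.2.2 | As normal | Yes, but not for this value |
| Scatterplot, SAP 12.2.3 | No | No |
| Summary statistics, SAP 12.2.1 | Yes | No |
| List by subject, SAP 13 | Yes | No |
| Adverse event tables, SAP 12.1.3 | If judged clinically significant | Yes |

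The gap is therefore the set of early values that return to normal and are not reported as adverse events.

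**3. Size of the shift-table gap.** Inputs: 60 per arm (protocol 7.6.1), and 31.6% as a stand-in for the proportion with abnormal TSH at any time. That figure is an adverse reaction rate, so using it this way is an assumption. The share q still abnormal at the last sample is not documented, so the full range is shown.

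Ever abnormal = 60 × 0.316 = 19.0. Shown in the shift table = 19.0 × q.

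| q | Shown | Missed by the shift table |
|---|---|---|
| 100% | 19.0 | 0 |
| 75% | 14.2 | 4.7 |
| 50% | 9.5 | 9.5 |
| 25% | 4.7 | 14.2 |
| 0% | 0 | 19.0 |

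These figures concern the shift table alone. Any of the missed subjects whose value is reported as an adverse event is still counted by that route, so the number missed by both counts is smaller by an amount the documents do not allow one to estimate.

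**4. Testosterone.** None of these inputs is in the documents; all are assumptions. Mean in men M = 4.5 ng/mL (SD 1.5), in women F = 0.2 (SD 0.1), proportion of men p = 60 to 80%, and a 25% fall in men only.

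- Pooled variance = p·1.5² + (1−p)·0.1² + p(1−p)(M−F)².
- At p = 0.6 before the fall: 1.35 + 0.004 + 0.24 × 4.3² = 5.79, SD 2.41. After the fall (M = 3.375): 1.35 + 0.004 + 0.24 × 3.175² = 3.77.
- Pooled difference = p × 0.25 × M = 0.6 × 1.125 = 0.675.
- Standardised difference = 0.675 / √((5.79 + 3.77)/2) = 0.31. In men alone it is 1.125/1.5 = 0.75.
- The same steps give 0.37 at p = 0.7 and 0.45 at p = 0.8.

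Pooling therefore keeps 0.31/0.75 = 41% to 0.45/0.75 = 60% of the standardised difference.

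**5. Sex mix as noise.** SD of the between-arm difference from chance imbalance = √(2p(1−p)/60) × (M−F). This is √(0.48/60) × 4.3 = 0.38 at p = 0.6 and √(0.32/60) × 4.3 = 0.31 at p = 0.8. The pooled differences, 0.675 and 0.8 × 1.125 = 0.90, are about 1.8 and 2.9 times as large. With a 20% fall they are 0.54 and 0.72, or about 1.4 and 2.3 times.

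**The case against.** A reader might infer that early endocrine abnormalities go uncounted altogether. The documents do not support that. The TSH figures from MR13A9-3 are themselves adverse drug reaction incidences, and the same route exists here. Protocol 9.12.1.3 counts as clinically significant any change the investigator considers beyond the subject's normal physiological variation, not only one that needs treatment. Such events are tabulated by preferred term and group from the start of treatment. Early values also enter the visit-wise summaries, with minimum, quartiles and maximum, and the by-subject list. This stands, and it confines the point to abnormal values not reported as adverse events.

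A reader might also infer that a testosterone effect is masked, or that the group mean mainly reflects sex mix. Step 5 of the working shows otherwise: the pooled difference exceeds the sex-mix noise in every scenario computed. Each group's Week 0 summary stands beside its later ones and largely removes a fixed imbalance. The scatterplots show individuals, and SAP Table 8.1-1 shows the sex mix. The documents do not say whether the low/normal/high limits are sex-specific, so nothing can be claimed about masking in the shift table. Dilution is what remains.

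Finally, the SAP follows protocol 13.6.3, which plans shift tables before and after treatment for all laboratory tests. There is no contradiction between the documents. No laboratory hypothesis test is planned, so no error rate or power is affected. All of this stands. It makes the point a reporting improvement but does not supply the missing count.

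**Conclusion.** The point holds as a minor reporting weakness. Followed as written, the plan gives no count by dose of measured early endocrine abnormalities that is independent of investigator judgement, and it gives a diluted comparison for testosterone and free testosterone.

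The size is uncertain. The shift table could miss anywhere from none to all of about 19 TSH cases per arm. That range assumes the earlier adverse reaction rate carries over as a laboratory abnormality rate, and it spans every possible persistence. If TSH stays abnormal to the last sample, nothing is lost. The rough halving for testosterone rests entirely on assumed means, spread, sex mix and a fall confined to men. The common reactions reported from the earlier studies in protocol 1.3.2.2 include no testosterone finding, so this part is a precaution.

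**What to change.** - **SAP 12.2.2:** for the endocrine tests, add shift tables from Week 0 to the lowest and to the highest on-treatment value over Weeks 1 to 8, by group. Keep the existing end-of-treatment table, and state whether the reference limits are sex-specific.
- **SAP 12.2.1:** for the endocrine tests, add change from Week 0 at each later time point, and present testosterone and free testosterone separately for men and women.

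The cost is a few extra tables from data already collected. A worst-value table also picks up random excursions, since each subject has up to four chances to cross a limit. The placebo group has the same sampling schedule and shows how often that happens by chance. Protocol section 13 already allows further necessary analyses, but naming these tables in the SAP fixes them before the results are seen.
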